6.2 Recruitment Strategy

SLHS routinely screens patients 12 years of age and older for suicide risk in EDs and primary care clinics. Patients who screen positive using the C-SSRS should complete a safety plan (moderate to high risk/provider judgment) or a connection and support plan (low risk/provider judgment) with a provider or clinical staff as part of standard of care. Following safety planning or connection and support planning, based on clinical judgment, patients should be introduced and invited to participate in the SPARC Trial by the provider or staff and may be given a brief hand-out describing the study. If the patient is interested in learning more, a video visit with a centrally-located Research Coordinator will be ordered through Epic or a phone call will be initiated to conduct informed consent and study enrollment.

Additionally, patients who express interest in the study but are unable to complete study enrollment and informed consent while in the clinic or ED may agree to be contacted by a Research Coordinator after they leave SLHS. In this case, study staff may contact the potential participant to review eligibility criteria, answer questions and gain informed consent. Study staff will reach out via text or email as soon as possible within 3 business days of the clinic or ED encounter to invite the potential participant to schedule a phone call or video visit. An opt out option (such as STOP or NONE) will be provided for individuals who do not wish to proceed, and the study team will not call potential participants who have not responded in writing to express interest in continuing. Study enrollment and informed consent will be conducted using videoconference or telephone to connect patients to centrally located study staff. All staff conducting informed consent and study enrollment will be trained in human subjects' protection and study procedures and will be delegated to do so by the study PI.

6.3 Retention

A variety of methods will be used to improve retention of research participants. A primary phone

number and an email address are required. Contact information will be collected at baseline, and participants may opt to share additional contact information (including alternative phone numbers, email addresses, or social media contact information) that may be used to contact participants for retention purposes. Email, text messages, phone calls, or other forms of contact may be used for retention purposes or to assist with scheduling and completing study surveys.

6.4 Populations for Analyses

Analyses will be completed using the following populations:

1. **Intention to Treat (ITT) Analytic Population:** Data for all participants that complete study enrollment will be included in this dataset.
2. **Safety Analysis Population:** The dataset shared with the Data & Safety Monitoring Board for safety analysis will include data for all participants who completed study enrollment (e.g., the ITT Analytic Population Dataset).
3. **Per-Protocol Analysis Population:** Data for a subset of participants who were retained for the duration of the study and completed the minimum assigned intervention (e.g. received at least one phone call (SPI+), or were sent at least 4 caring contacts (SP+CC)).
4. **Additional Populations:** Additional datasets may be developed to complete sensitivity analyses, for example, where missing data have been imputed using different techniques.

7. Study Procedures

Pre-Consent – All participants (All activities are standard of care)

- C-SSRS screening for suicide risk at clinic or ED visit
- Development of safety plan or a connection and support plan

Baseline / Enrollment Visit – All participants (During/following clinic or ED visit)

- Study enrollment and informed consent
- Baseline Survey
 - Baseline survey includes questions related to demographics, socioeconomic status, gender identity, sexuality, religion, drug and alcohol use, quality of life, loneliness, self-harm and suicidal behavior.

Follow-Up Intervention – SPI+ participants

- Follow-up phone calls from the Hotline
 - 1 call within 72 hours of study enrollment to connect with the participant.
 - Series of 1-6 phone calls, based on participant's preference.
 - See *Description of Interventions*.

Follow-Up Intervention – SP+CC participants

- Follow-up phone call and caring text or email messages from the Hotline
 - 1 call within 72 hours of study enrollment to connect with the participant.
 - 25 personalized caring text or email messages sent according to a standardized schedule over a 12-month period.
 - See *Description of Interventions*.

2-Week Patient Satisfaction Survey – All participants (REDCap survey link sent via text or email)

- Patient satisfaction survey related to intervention received

6 Month Outcome Assessment – All participants (+ 4 weeks variance window) (REDCap survey link sent via email or text, or phone call)

- 6-Month Outcomes Survey
 - Outcomes survey includes loneliness, suicide risk, self-harm and suicidal behavior, behavioral health treatment.

12 Month Outcome Assessment – All participants (+ 4 weeks variance window) (REDCap survey link sent via email or text, or phone call)

- 12-Month Outcomes Survey
 - Outcomes survey includes loneliness, suicide risk, self-harm and suicidal behavior, behavioral health treatment, and patient satisfaction.

Assessing Provider Satisfaction (Aim 2)

Providers and staff in study sites will be emailed an invitation to complete a survey during year 1 or 2 of the study. Providers and staff will complete surveys using a REDCap link delivered via email. A statement will be included in the survey invitation email indicating that opening the link and completing the survey constitutes provider/staff consent to participate in the survey. These surveys will be confidential and no personal health information will be collected.

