Description of Study Sites	A total of 32 study sites were selected within St. Luke's Health System in Idaho. Randomization will occur at the individual level. Study sites include 9 EDs and 23 primary care clinics.

Study Duration This study will last for 3 years, with survival assessed for up to 10 years.

Participant Duration Participants will be followed for 12 months. Participants will complete assessments at baseline, 2 weeks, 6 months, and 12 months.

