10.5 Definition of Minimal Intervention

To be considered a recipient of the study interventions, participants must have completed a connection and support plan or a safety plan at St. Luke's. If randomized to the SPI+ comparator, participants must receive at least one phone call from the Hotline. If randomized to the SP+CC comparator, participants

must be sent at least 4 caring text or email messages.

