14.1 General Analytic Approach

The primary analysis will compare the effectiveness of the two interventions delivered in the two settings (EDs and primary care), accounting for the other covariates of interest. Potential confounding, effect modification, and mediation will be handled through study design (e.g. individual randomization), through stratification (age category), and use of multilevel modeling to account for geographic clustering. Other published studies related to caring contacts and safety planning with and without follow-up have shown that the selected patient-centered outcomes change over a 6-12-month period in response to receipt of these interventions.^{24,63}

All data analyses will be completed using appropriate statistical software (such as R and R Studio, SPSS, Stata, SAS, Python, and/or Microsoft Excel).

Statistical significance will be determined based on a type I error (alpha) of 0.05 (two-sided). Confidence intervals will be reported in addition to p-values.

Aim 1: Analyses will be stratified for adults and adolescents, modeling the effects of intervention separately in these age groups. There is very little evidence regarding the effect of safety planning, caring contacts, or follow-up phone calls on adolescent populations, and we hypothesize that the magnitude of effect may differ by age group. Generating evidence of the effectiveness of these interventions in suicidal adolescents is the primary goal of this heterogeneity of treatment effect (HTE) analysis. **Appropriate statistical analyses will be used to determine whether outcomes differ between the intervention arms.**

Interaction between the interventions and settings will be assessed. Variables will be measured at baseline and reported using descriptive statistics. Potential effect modifiers will be assessed and include age, sex, gender identity, sexuality, race/ethnicity, religion, urban/rural residence, drug/alcohol use,

suicidal ideation and behavior at baseline, baseline quality of life, baseline loneliness, medication use, measures of socioeconomic status and/or other variables related to the specified outcomes of interest. Data will be analyzed according to both an intention to treat protocol and per protocol received. Please see section 5.4 Populations for Analyses for further detail.

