17.13 Assessing Long-Term Survival

One important outcome of interest in any suicide prevention research is death by suicide. Given the rare nature of this event, we would not expect to see a significant difference in this outcome between the two intervention groups over the duration of this three-year study, thus we have not included death as a primary or secondary outcome for this study. However, the study team plans to follow-up on participants over time in order to assess the effect of these interventions on death by suicide over a 5- 10 year period. National Death Index Plus data from CDC will be obtained for the purpose of assessing death and cause of death of participants enrolled in the study. These data will be accessed only for those participants who are defined in the ITT and the Per-protocol populations for up to ten years following study enrollment.

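### The per-protocol set depends on an undefined retention condition which, read plainly, excludes suicides before month 12 and late withdrawals

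*Protocol*

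**What the plan says.** Section 6.4 lists the analysis populations. For ITT, "Data for all participants that complete study enrollment will be included in this dataset", and the safety population is the same set. The per-protocol population is "Data for a subset of participants who were retained for the duration of the study and completed the minimum assigned intervention", where the minimum is at least one call (SPI+) or at least four messages sent (SP+CC). Both conditions must be met.

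Section 10.5 sets the same minimum with no mention of retention: "To be considered a recipient of the study interventions, participants must have completed a connection and support plan or a safety plan", plus the call or the four messages.

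Section 14.1 commits to using the set: "Data will be analyzed according to both an intention to treat protocol and per protocol received".

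Section 17.13 plans long-term follow-up through the National Death Index "in order to assess the effect of these interventions on death by suicide" over 5 to 10 years. On populations it says: "These data will be accessed only for those participants who are defined in the ITT and the Per-protocol populations", for up to ten years from enrollment.

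On duration, the synopsis (1.1) says "Participants will be followed for 12 months". Section 11.3 counts a person as lost only if both follow-up assessments are missed and at least three contact attempts fail. Section 11.2 allows withdrawal on written request at any time. No section defines retained or says how a death counts.

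**The concern.** A per-protocol set should be defined by whether the assigned intervention was received. Section 6.4 adds a condition that is known only at the end of follow-up and that the outcome itself can determine, since a person who has died cannot be retained.

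Two consequences follow on the plain reading. First, the set contains no suicide before month 12 in either arm, although section 17.13 links it to an analysis whose clock starts at enrollment. Those are the months in which calls and messages are delivered. An effect confined to that period would not show in a per-protocol survival result, and the per-protocol count of suicides would be too low.

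Second, the primary outcome is measured at 6 and 12 months (9.2). A person who withdraws in writing in month 8 has a valid 6-month score, but leaves the set on which the 6-month per-protocol comparison is made. That comparison is then conditioned on behaviour after the measurement.

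**Working it through.** The protocol gives no figure to reproduce here. The check sets the sections side by side and then illustrates the mechanism with assumed counts.

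**1. Who is in which set.** Suppose each participant below received the section 10.5 minimum. Study duration is read as the 12 months of participant follow-up.

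| Participant | ITT and safety (6.4) | Recipient (10.5) | Per-protocol (6.4) |
|---|---|---|---|
| Dies by suicide in month 3 | in | yes | out, on the plain reading |
| Completes month 6, withdraws in writing in month 8 | in | yes | out |
| Completes month 6, misses month 12, does not withdraw | in | yes | unclear |
| Misses both surveys, cannot be reached | in | yes | out (withdrawn under 11.3) |

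The third row is unclear because section 11.3 does not count this person as lost. On the other side, section 12.2 has the DSMB review retention at 6 and at 12 months, and section 17.7 labels the 12-month payment as study completion. The first two rows do not depend on which reading is taken.

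**2. What excluding early deaths can do.** All death counts here are assumed. Equal arms give 1,382 / 2 = 691 each. Let E be deaths before month 12 and L later deaths, with subscripts for arm. Everyone except those who die early is taken to be in the per-protocol set.

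- ITT ratio = [(E1 + L1) / 691] / [(E2 + L2) / 691]
- Per-protocol ratio = [L1 / (691 − E1)] / [L2 / (691 − E2)]

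| E1, E2 | L1, L2 | ITT ratio | Per-protocol ratio | Deaths lost |
|---|---|---|---|---|
| 1, 1 | 6, 6 | 7/7 = 1.00 | (6/690)/(6/690) = 1.00 | 2 of 14 |
| 2, 5 | 8, 8 | 10/13 = 0.77 | (8/689)/(8/686) = 1.00 | 7 of 23 |
| 1, 6 | 7, 7 | 8/13 = 0.62 | (7/690)/(7/685) = 0.99 | 7 of 21 |
| 3, 3 | 7, 10 | 10/13 = 0.77 | (7/688)/(10/688) = 0.70 | 6 of 23 |

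Unequal early deaths (second and third rows) can erase an early effect. Equal early deaths leave the difference in deaths unchanged: in the last row it is 10 − 13 = −3 under ITT and 7 − 10 = −3 per protocol. The ratio can still move, from 0.77 to 0.70, because the per-protocol set describes only the later period. In every row the per-protocol count is too low.

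**3. What the protocol allows on numbers.** Section 14.2 allows up to 30% dropout: 0.30 × 1,382 = 414.6, about 415. It does not say how many of these would have a 6-month score. If 0, 25, 50, 75 or 100% did, and all of them counted as not retained, the usable 6-month scores dropped would be 0, 104, 207, 311 or 415. So wide a range is not an estimate.

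**The case against.** The strongest reply is that this is a companion analysis and nothing is hidden. ITT and the safety population keep every early death and every 6-month score. The DSMB reviews death by suicide by arm (12.2, 12.3), and every death is reviewed for cause (12.4). Section 17.13 states that death is neither a primary nor a secondary outcome. Restricting a per-protocol set to completers is a common, if criticized, choice, and sections 6.4 and 10.5 define different things. All of this stands, and it limits the point to the per-protocol results.

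It can also be said that section 17.13 only states whose death data will be accessed, with no per-protocol survival model, and that no section says a death is non-retention. Both statements are correct, so the exclusion is a plain reading and not a stated rule. But the per-protocol set is a subset of ITT, so naming it for access alone would add nothing. Its natural purpose is analysis.

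Four stronger inferences are tempting, and the protocol does not support them:

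- *Everyone who misses month 12 loses their 6-month outcome.* Under section 11.3 such a person is not lost to follow-up and may count as retained.
- *About 415 participants leave the set because of this clause.* That is the maximum dropout allowance. Some of those people would have no outcome to discard, and some would fail the minimum intervention anyway.
- *Retention will differ by arm because SP+CC messages run to month 12.* Surveys and payments are the same in both arms. Table 1 shows SPI+ calls up to 6 months, and section 10.2 permits additional calls. No direction can be predicted.
- *The trial cannot see suicides in the first year.* Only the per-protocol set is affected.

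**Conclusion.** The point holds in a limited form. Section 6.4 fixes per-protocol membership on an undefined post-randomization condition that is related to the outcome and absent from section 10.5. Read plainly, it removes suicides before month 12 from a population that section 17.13 names for assessing suicide, and it removes people who formally withdraw between months 6 and 12 with a valid 6-month score. The status of a participant who only misses the month-12 survey cannot be determined from the text.

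The effect is confined to the per-protocol analyses. The difference between arms is distorted only if early deaths or late withdrawals differ by arm, in number or in the kind of participant. A ratio can also shift when early deaths are equal but later ones are not. The size cannot be derived from the protocol, and the counts in the working only show the mechanism. The conclusion assumes that study duration means the participant's 12 months and that a person who has died is not retained. This is a stated rule that works badly, not a detail left to the statistical analysis plan.

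**What to change.** In section 6.4, delete the retention condition and define the per-protocol set by the section 10.5 minimum alone. Use the outcomes available at each time point and handle missing ones as in section 14.3. If the team wants to keep retention, apply it separately at 6 and 12 months, define it consistently with section 11.3, and state that deaths stay in the set as events.

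In section 17.13, state that ITT is the population for death by suicide. If a supportive per-protocol survival analysis is kept, decide membership by what was received up to a common early landmark and start the clock there. The protocol's schedules make this workable: the first call is aimed at 72 hours, and three messages fall in the first week before weekly ones begin, so the fourth is due soon after. A landmark is needed even without the retention clause, because a participant must survive long enough to receive the minimum.

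The cost is a few sentences and no new data. The per-protocol set will be larger and will contain some missing outcomes.

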7.1 Schedule of Activities

Table 1: Schedule of SPARC Trial Activities

	Time Point 1: Study Enrollment & Baseline	Time Point 2: ~72 hours following study enrollment	Time Point 3: Week 1 – 6 months	Time Point 4: 2 weeks	Time Point 5: 6 months	Time Point 6: 6-12 months	Time Point 7: 12 months	Timepoint 8: Year 1 or 2
--	---	--	---------------------------------	-----------------------	------------------------	---------------------------	-------------------------	--------------------------

Informed Consent/Assent	X							
SPARC Baseline Survey	X							
6-month Outcome Survey					X			
12-month Outcome Survey							X	
Phone call with Hotline (scheduled/initiated)		X	SPI+ arm only					
Caring text or email messages sent from Hotline		CC+ arm only	CC+ arm only			CC+ arm only		
Patient satisfaction survey				X			X	
Provider satisfaction survey								X
Safety Outcomes reporting					X		X	

8. Causal Framework

The causal mechanisms of suicide are complex and are not well understood, particularly those responsible for the transition between suicidal ideation and action.^{29,30} The National Institute of Mental Health (NIMH) has developed a framework for developing novel interventions to prevent or treat mental health disorders that they call the Research Domain Criteria (RDoC).^{31,32} NIMH RDoC have not been enumerated specifically for suicide.³⁰ To conceptualize the hypothesized causal pathways between the two evidence-based interventions (SPI+ and SP+CC) and suicidal ideation and behavior, we borrowed pertinent constructs from the general behavioral health RDoC and embedded these within a Social-Ecological Model³³ (SEM). Both SPI+ and SP+CC are complex interventions that act upon multiple domains and constructs. Safety planning includes six distinct elements; SPI+ follow-up includes at least one Hotline phone call; SP+CC includes one Hotline phone call and a series of caring text messages. The table below describes how the various elements of safety planning and structured follow-up relate to selected domains and constructs. The NIMH RDoC also include physiological and biological domains that are relevant to suicidal causal pathways; however, we have excluded these domains here because the compared interventions do not act directly on those levels.

[figure not shown]
Table 2: Mapping Elements of the SPARC Trial Interventions onto the Social-Ecological Model (SEM)

PSYCHOLOGICAL / INTRAPERSONAL DOMAIN	
Internal thoughts & feelings	Safety Planning Element #1: Warning signs (thoughts, mood, images, behavior) that a crisis may be developing
Behavior	Follow-Up: Caring Contacts text messages aim to make patients feel supported and cared for Safety Planning Element #2: Coping strategies and distractions (things I can do to take my mind off my problems without other people (meditation, physical activity, etc.))
INTERPERSONAL DOMAIN	

Social support and Affiliation & Attachment	
Safety Planning Element #3: People and social settings that provide distraction
 
Safety Planning Element #4: Trusted people whom I can ask for help
 
Follow-Up: Hotline Phone Call(s) provides opportunity to receive social support from Hotline follow-up specialists
 
Follow-Up: Caring Contacts text messages provide non-demanding messages of social support

Professional support	
Safety Planning Element #5: Professionals or agencies I can contact during a crisis
 
Follow-Up: Hotline Phone Call(s) Hotline follow-up specialists are trained to provide support to suicidal individuals
 
Follow-Up Hotline Phone Calls(s) Hotline staff counsel patients on how to navigate barriers to seeking care

ENVIRONMENTAL DOMAIN	
Making environment safe	
Safety Planning Element #6: Restricting lethal means
 
Follow-Up Hotline Phone Call(s) Hotline staff reinforce the importance of lethal means restriction and this is a key focus of the phone call(s)

The causal framework below depicts the hypothesized and known associations for variables included in this study. All variables included in the causal framework will be measured. The associations depicted with solid arrows are assumed to be true based on empirical evidence (described in the paragraphs that follow the framework); associations depicted with dashed lines are hypothesized and will be assessed and measured as part of this study. The bracket around the population variables was added to visually simplify the framework; it represents solid arrows from each of the variables under population to each of the baseline characteristic variables.

Figure 2: SPARC Trial Causal Framework

9. Exposures and Outcomes (Variables) of Interest

9.1 Exposure Variables

The following exposure variables will be measured and assessed as part of this study: age, sex, gender identity, sexuality, race, ethnicity, religious affiliation, religious behavior, socioeconomic status (including income, education, employment, and insurance type), rural/urban residence, alcohol use, overall health / presence of co-morbidities, medication use, marijuana, and illicit drug use. A full summary of exposure, outcome, and process variables to be collected as part of this study is included in *Table 4: SPARC Trial Variables of Interest and Other Data Elements*. Key exposure variables known to influence suicide risk will be collected to evaluate potential differential distribution among intervention groups, which may not be perfectly controlled for randomization.

